For a two-sample pooled t-test of a normal mean difference with a two-sided significance level of 0.05 ($P<0.05$), assuming a common standard deviation of 2 on the 0-10 FIQR pain numeric rating scale, a total sample size of 200 assuming a balanced design (1:1), will have statistical power of 0.94 (94%) to detect a difference between the means of say 6 and 7. Even with a smaller sample of 128 patients in the ITT population assuming a balanced design (1:1), the statistical power of the suggested minimum 80 % will be obtained, to detect a difference between means of 1 on the 0-10 pain numeric rating scale. Since some attrition, drop-outs and missing data was expected during the 24-week intervention period, we decided to include 200 participants (approximately 100 in each group), in the ITT population, corresponding to a statistical power of more than 90% to detect a difference between groups that patients in the ITT population will perceive as important (4).

Statistical interim analyses and stopping guidance

No interim analyses are carried out. Due to the Covid-19 pandemic and long-term illness among the project staff, the inclusion period was extended by an extra year to allow for the inclusion of 200 participants and better ensure achieving the prespecified sample size of 200 patients in the ITT population.

Timing of final analyses

The primary and key secondary outcomes are analyzed collectively and will be reported in the primary manuscript. Final analyses will be performed blinded to group allocation and after the last patient- last- visit has been performed and all week-36 follow-up data are collected (expected in February 2024).

Box 1: Visit schedule for enrolment, interventions, and assessments. Visit “window” +/- 7 days

	STUDY PERIOD										
	Enrolment	Allocation	Post-allocation								Follow-up
Week	-8 - 0	0	1*	2	4	8*	12	16*	20	24	36
ENROLMENT:											
Informed consent	x										
Eligibility screen	x										
Medical/medicine history	x										
Physical examination	x									x	
INTERVENTIONS:											
Cannabidiol (CBD)			↔								
Placebo			↔								
Medicine dispensation		x			x		x		x		
ASSESSMENTS:											
Vital signs: BP, pulse	x	x		x	x		x		x	x	x
ECG	x										
Safety tests: Hematology, Electrolytes, ALAT, Alkaline phosphatases, Bilirubin, CRP, Urine HCG, Opioids, THC	x						x			x	
Proms: FIQ-R, PSQI, EQ5D, ADL-Q, PSEQ, DASS-21, PSS, C-SSRS, SNAQ, FSHSS		x			x		x		x	x	x

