Robustness is a concept that refers to the sensitivity of the overall conclusions to various limitations of the data, assumptions, and analytic approaches to data analysis. Robustness implies that the treatment effect and primary conclusion of the CANNFIB trial is not substantially affected when analyses are carried out, based on alternative assumption or analytic approaches (11).

Harms

Data on adverse events (AE) are collected at all visits up to 36 weeks from baseline. The participants are interviewed about any adverse events occurring during the trial. We will provide information about the severity of the adverse event, and the action taken with regards to the AE i.e., whether any concomitant medication was taken, dose reduction or whether the study drug was paused, discontinued or if other actions was taken. The study physicians assess whether the AE is expected and possible relation to the study drug, based on the Summary of Product Characterizing for CBD as a reference document. The Common Terminology Criteria for Adverse Events (CTCAE version 5.0 will be used as the reference document for graduation the severity of the AE and whether the AE is a Serious Adverse Event (SAE). Harms observed in 5% or more in the study population are reported in this study. Based on the ITT population, the following safety data will be summarized in the final analysis report:

- All adverse events are summarized with a breakdown of severity categories (mild, moderate, severe, and serious), for both treatment arms
- The number and percentages of participants who withdraw from the intervention because of adverse events are reported for both treatment arms.

Statistical software

All analyses will be performed using the statistical software SAS version 9.4 (SAS Institute, Cary, NC, USA).

Figures and Tables Outline

Figure 1. Trial Profile: Patient Flow Throughout the Final Trial

Table 1. Baseline Characteristics for the Intention-To-Treat Population

Table 2. Primary and Key Secondary outcomes at 24 weeks from Baseline in the ITT Population

Figure 2a. The average trajectory in each group for the Pain Intensity (Average pain during the last 7 days) over time from baseline (week 0) to endpoint (week 24) and follow-up (week 36)

Figure 2b. Scatterplot of the individual values of after vs baseline in pain intensity in the intervention group and placebo group from before (at baseline) and after the intervention (at week 24).

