8.1 Examinations and testing

Participants will be subjected to a variety of examinations, questionnaires and testing during screening, enrolment and allocation, medical intervention visits, end of treatment and end of trial visits, (see table 1; visit schedule). Blood testing with standard biochemistry (C-reactive protein, Alanine Aminotransferase, Alkaline phosphatases, bilirubin, calcium, creatinine, potassium, sodium and hematology (hemoglobin, leucocytes, differential cell count, erythrocyte, erythrocyte volume fraction, erythrocyte middle volume, erythrocyte middle cell hemoglobin concentration, thrombocytes, reticulocytes), will be performed at screening visit, week 12 and week 24. Blood samples are drawn in order to monitor participants' liver and kidney function, inflammation markers and overall hematology, for safety. The sample will contain 10 ml of blood and will be destroyed after analysis. Urine samples for pregnancy tests and screening for Cannabinoid (THC) and opioid concentration in the urine, will be performed for safety and to ensure that participants are complying with the study protocol. The sample will contain 100 ml of urine and will be destroyed after analysis. Vital signs including blood pressure, systolic and diastolic and resting pulse (sitting down) will be monitored at all visits. ECG (12-lead) will be assessed at the screening visit. Participants will also undergo screening for potential psychiatric side effects including suicide risk, at the screening visit.

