11. SAFETY CONSIDERATIONS

11.1. Potential side effects, risks, and discomforts for study subjects

Common side effects (1-10%) of drugs containing both THC and CBD (Sativex), are overall feeling of weakness and uneasiness, reduced or increased appetite, diarrhea, nausea, dryness in the mouth, constipation, apathy, balance problems, depression, euphoria, feeling of intoxication, problems with memory and concentration, confusion, personality disorders, sleepiness, difficulty speaking, blurred vision. Rare side effects (0,1-1%) are abdominal pain, hypertension, hallucinations, psychosis, suicidal behavior and fainting. THC and CBD may interact with and enhance the effects of sedatives and alcohol [60]. According to the current legal practice in Denmark, it is not allowed to drive a car when using medical THC. CBD alone is shown to have a favorable safety profile compared to the CBD + THC combined or THC alone.

The most commonly reported side effects of CBD (seen in at least 10%), are tiredness/fatigue, problems sleeping, feeling weak, changes in appetite and weight, infections, diarrhea and rash [61]. More serious and rare side effects (seen in at least 1 %), are hypersensitivity reactions, hepatocellular injury and suicidal behavior and ideation [62]. However, these serious side effect have been reported in patients diagnosed with epilepsy who have been undergoing treatment with daily Cannabidiol dosages of 5 mg per kilogram body weight [62], which could be six times the dosages prescribed in the current CANNFIB study.

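### The planned safety output has no by-arm summary of the liver tests or the C-SSRS, and would not name hepatic or suicidal events seen in fewer than 5% of the pooled population

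*SAP*

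**What the plan says.** **Risks named.** Protocol 11.1 says that the more serious side effects of CBD, seen in at least 1%, "are hypersensitivity reactions, hepatocellular injury and suicidal behavior and ideation". It adds that these were reported in patients with epilepsy on 5 mg per kg daily, possibly six times the dose used here.

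**Data collected.** Box 1 of the SAP schedules "Safety tests: Hematology, Electrolytes, ALAT, Alkaline phosphatases, Bilirubin, CRP" and further tests at screening, week 12 and week 24. Protocol 8.1 gives the reason: "Blood samples are drawn in order to monitor" liver and kidney function, among other things, for safety. Box 1 places the C-SSRS with the patient-reported measures at weeks 0, 4, 12, 20, 24 and 36.

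**Output planned.** Under Harms, the SAP describes how adverse events are gathered ("The participants are interviewed about any adverse events occurring during the trial"), limits reported harms to those seen in at least 5% of the study population, and then says "the following safety data will be summarized in the final analysis report". Two items follow: adverse events by severity and arm, and withdrawals from the intervention because of adverse events. The Table 3 shell adds exposure time, event rate per patient-week, serious adverse events, deaths, and named events in at least 5% of the ITT population. Its named rows include depressed mood and anxiety or distress, but nothing hepatic and nothing on suicidality.

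**The concern.** Safety is part of the stated aim (SAP, Aim and Objectives; protocol 4.4). For two of the serious risks that the protocol names, the trial schedules a repeated measurement in both randomised arms: two post-baseline liver panels and five post-baseline C-SSRS assessments per patient. Neither measure appears in an endpoint list, an analysis section or a table shell of either document.

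An adverse-event table is an indirect substitute. Neither document states what ALAT value or C-SSRS answer becomes an adverse event, so capture rests on case-by-case judgement. An event that is captured then loses its name if it falls below the 5% cut. The safety conclusion of the main report could therefore be drawn without the by-arm comparison that these measurements make possible.

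**Working it through.** **Plan's own figures.** The plan gives no calculation for safety. Its sample size supplies the denominators: 200 participants, 1:1, so 100 per arm. The stated power for pain (difference 1, SD 2, two-sided 0.05) reproduces: the pooled t-test gives 0.940 at N = 200 and 0.801 at N = 128, against 0.94 and 0.80. That calculation is not in dispute.

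**Step 1: collection against output.**

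| Named risk (protocol 11.1) | Scheduled measure | By-arm summary planned |
|---|---|---|
| Hepatocellular injury | ALAT, alkaline phosphatases, bilirubin: screening, weeks 12, 24 | None |
| Suicidal behaviour and ideation | C-SSRS: weeks 0, 4, 12, 20, 24, 36 | None |
| Hypersensitivity | No dedicated instrument | Adverse-event rows only |

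**Step 2: the 5% rule.** The threshold is 0.05 × 200 = 10 participants. If an event occurs only on CBD, with X ~ Binomial(100, p), it earns a named row with probability P(X ≥ 10). If both arms share rate p, X ~ Binomial(200, p). The rates below are assumptions.

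| True rate p | CBD only, P(X ≥ 10 of 100) | Both arms, P(X ≥ 10 of 200) |
|---|---|---|
| 1% | < 0.0001 | < 0.0001 |
| 3% | 0.0009 | 0.08 |
| 5% | 0.028 | 0.55 |
| 10% | 0.55 | 0.996 |

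The SAP applies the cut to the ITT population as a whole. If it were applied within the CBD arm instead (5 of 100), the chances would be 0.003, 0.18, 0.56 and 0.98.

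**Step 3: a concrete split.** Nine CBD cases and no placebo cases total 9, below 10, so there is no named row. The one-sided Fisher probability is C(100,9)/C(200,9) = 0.0016, and the equal arms double it: two-sided P = 0.0032. The Newcombe 95% interval for the risk difference is 3.4% to 16.2%.

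**Step 4: at 1%.** Expected CBD cases are 0.01 × 100 = 1. The chance of at least one is 1 − 0.99^100 = 0.63. A case recorded as an adverse event would show only in the aggregate rows.

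**Step 5: what a by-arm table could show.** With 0 of 100, the two-sided exact 95% upper limit is 1 − 0.025^(1/100) = 3.6%. The 95% half-width for a difference in mean laboratory values is t(0.975; 198) × √(2/100) = 0.28 SD. Power with 100 per arm is about 38% for 1% against 5%, and about 80% for 1% against 10%. The table would be descriptive, not confirmatory.

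**The case against.** A reader might infer that the report counts only adverse events and withdrawals, or that it cannot address liver injury or suicidality at all. The documents do not support either reading.

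- Table 3 also has exposure, event-rate, serious-event and death rows. The Harms text also promises severity and action taken, and has physicians assess expectedness and relatedness.
- Protocol 8.3 and 11.2 provide for laboratory as well as clinical evidence of adverse events. A hepatic or suicidal event recorded that way enters the totals and severity rows by arm, and the serious-event row if it qualifies. The 5% cut governs only the named rows.
- Protocol 15.3 plans a separate safety paper.

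On importance, the named risks were reported at higher doses in epilepsy. Eligibility excludes impaired liver and kidney function, epilepsy, major depressive disorder and past suicidal behaviour. Protocol 8.1 presents the blood tests as monitoring, and neither document promises a group comparison of them.

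These points narrow the concern without removing it. Entering a total is not the same as being identified. The safety paper has no stated laboratory or C-SSRS analysis. Low expected rates limit what the table can prove, but they also make the 5% cut most likely to hide these events. It would also be wrong to treat 1% as a ceiling: the protocol says at least 1%, and the dose caveat may lower the rate here by an unknown amount.

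**Conclusion.** The point holds as a gap in planned reporting. The SAP plans adverse-event tabulations and no by-arm summary of the liver tests or C-SSRS. Hepatic or suicidal events recorded as adverse events would be counted, but named only at 10 or more of 200 participants. An event confined to CBD at a true rate of 5% would get a named row with probability of about 0.03, and a 9 against 0 split would get none.

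This rests on 100 patients per arm, on the pooled reading of the 5% rule, and on illustrative event rates. Efficacy inference is unaffected. One limit applies: the SAP cites protocol version 5, while the protocol supplied is version 4, so an addition in version 5 cannot be excluded. The omission from the SAP itself stands.

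**What to change.** Add one descriptive table by arm, without tests, to the Harms list:

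1. ALAT, alkaline phosphatases and bilirubin at screening, week 12 and week 24, with the number of patients moving from normal to above the laboratory's upper limit, and by CTCAE grade. The SAP already uses CTCAE version 5.0.
2. The number of patients with any post-baseline C-SSRS ideation or behaviour, and the number in whom it is new since baseline. State that baseline is week 0: protocol 8.1 puts suicide-risk screening at the screening visit, whereas the schedule starts the C-SSRS at week 0, and the two should be reconciled.
3. Adverse events matching the risks named in protocol 11.1, including hypersensitivity.

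Report all three regardless of the 5% cut, with two-sided exact 95% confidence intervals for the proportions, in line with the SAP's two-sided convention.

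The cost is a slightly longer safety report from data already collected. No visit, test or alpha is added, and precision remains descriptive only.

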The CONSORT flow diagram (Figure 1), includes information about the number of people recruited, screened, eligible, consented, randomized, allocated to treatment, withdrawal from treatment and lost to follow-up from baseline to week 36.

Withdrawals and follow-up

The CONSORT flow diagram (Figure 1) displays the number of participants lost to follow-up for the following time points; week 4 visit, week 12 visit, week 20 visit, week 24 visit (primary endpoint assessment), and week 36 visit. The reason for loss to follow-up will be reported as either due to adverse event or due to other reasons. The level of withdrawal will be categorized as withdrawal from the intervention, withdrawal from follow-up, or complete withdrawal.

Baseline characteristics

Baseline characteristics for each treatment arm will be summarized to visualize whether relevant demographic, pain-related, and other relevant characteristics appear balanced across the two groups. These data will be presented in the primary manuscript as shown in Table 1. Categorical data will be described using numbers and percentages. Normally distributed continuous data will be described using means and standard deviations (SDs), whereas continuous data that appear skewed will be described using medians and interquartile ranges.

Analysis

Outcome measures

A clinical trial's endpoints measure the outcomes in the trial. The following outcomes are applied in this study assessed 24 weeks from baseline.

Primary endpoint

Change in the pain intensity subscale of the Fibromyalgia Impact Questionnaire Revised (FIQ-R) from baseline to week 24.

Key secondary outcomes

Changes from baseline to week 24

- Sleep quality measured with the Pittsburgh Sleep Quality Index, total score of overall sleep quality. Scores are ranging from 0 to 21, with lower scores indicating better sleep quality and higher scores indicating worse sleep quality.
- Sleep duration measured with the Pittsburgh Sleep Quality Index, sleep duration domain, with number of hours of actual sleep during the night.
- Objectively measured sleep duration with number of minutes of nightly rest, measured with the Sens triaxial accelerometer device; MOTION® activity and rest measurement system.
- Objectively measured sleep patterns measured with the Sens triaxial accelerometer device; MOTION® activity and rest measurement system, in which movements during the night the number of times getting up during the night are indicated.

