Sleep quality, PSQI 0-3			
Sleep duration, PSQI 0-3			
Observed sleep duration SENS, number of minutes			
Observed sleeping patterns, SENS number of awakenings			
Performance-based activities of daily living, AMPS ADL motor ability, Logits			
Performance-based activities of daily living, AMPS ADL process ability, Logits			
Self-reported activities of daily living, ADLQ, Logits			
Quality of life, EQ5D global VAS 0-100			
Energy, FIQ NRS 0-10			
Responder indices:			
> 1 unit improvement in FIQ-R pain, n (%)			
≥ 30 % improvement in FIQ-R pain, n (%)			
≥ 50 % improvement in FIQ-R pain, n (%)			

Figure 2a. The trajectory for the Pain Intensity (Average pain during the last 7 days) over time from baseline (week 0) to endpoint (week 24) and follow-up (week 36)

[figure not shown]

Figure 2a. Scatterplot of the individual values of level of pain intensity in the intervention group and placebo group from before (at baseline) and after the intervention (at week 24).

[figure not shown]

Figure 3. Forest plot of standardized mean differences from baseline to week 24 in Primary and Key Secondary outcomes.

[figure not shown]

Table 3. Harms: Adverse Events in Total and observed in at least 5% ITT population up to 36 weeks from baseline

Exposure time, patient weeks	Total	CBD	Placebo
AE n patients (%)			
AE n events (rate per patient week)			
AE mild, n patients (%)			
AE moderate, n patients (%)			
AE severe, n patients (%)			
Withdrawals due to AE, n (%)			
SAE, n (%)			
Deaths, n patients (%)			
Observed AEs in at least 5 % of the ITT population			
Central nervous System			
• Dizziness (n)			
• Headaches/migraines (n)			
• Sensory disturbances (n)			
Psychological/cognitive			
• Depressed mood (n)			
• Anxiety/distress (n)			
Cardiac system			
• Palpitations (n)			
• Hot flashes (n)			
Gastrointestinal system			
• Nausea/vomiting (n)			
• Diarrhea (n)			
• Constipation (n)			
• Stomach pain (n)			
• Increased appetite (n)			
• Decreased appetite (n)			
Skin and mucus membranes			
• Dryness of mouth/throat (n)			
• Hair loss (n)			
• Itchy skin(n)			
• Rash (n)			
Infections			
• Covid-19 infection (n)			
• Common cold (n)			
• Influenza (n)			
• Gastroenteritis (n)			
Musculoskeletal system			
• Worsening in pain (n)			
General events			
• Worsening in fatigue (n)			
• Worsening in sleep disturbances (n)			

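### Table 3's aggregate adverse event rows count worsening of pain, the primary outcome, so a pain benefit of CBD could partly mask an excess of other adverse events in those rows

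*SAP*

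**What the plan says.** The Harms section of the SAP sets the rule for the totals: "All adverse events are summarized with a breakdown of severity categories (mild, moderate, severe, and serious), for both treatment arms". No term is excluded. The Table 3 shell turns this into rows by arm for patients with any AE, for events ("AE n events (rate per patient week"), and for patients in each severity grade (the first is "AE mild, n patients").

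Further down, under the heading "Observed AEs in at least 5 % of the ITT population", the shell lists the individual terms. Among them are "Worsening in pain (n", a corresponding line for fatigue, and "Worsening in sleep disturbances (n". These terms are therefore AEs in the plan's own sense and enter the aggregate rows.

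The primary endpoint is given in the SAP as "Change in the pain intensity subscale of the Fibromyalgia Impact Questionnaire Revised (FIQ-R) from baseline to week 24". Sleep outcomes are key secondary in both documents. Fatigue is not a named outcome. The nearest is FIQ-R energy level, which is key secondary in the SAP and exploratory in protocol section 9.4.

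Protocol section 11.1 also says: "The most commonly reported side effects of CBD (seen in at least 10%), are tiredness/fatigue, problems sleeping". Worsening of pain is not in that section's list of CBD side effects.

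The Harms section has AEs collected up to week 36, which includes 12 weeks without study drug. Study physicians assess relation to the study drug, but Table 3 has no row for related AEs. Neither document says when worsening of fibromyalgia pain counts as an AE, and neither plans a total without it.

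**The concern.** The trial aims to compare both efficacy and safety with placebo. A patient whose pain gets worse can enter the trial twice: as a poor result on the primary outcome, and as a patient with an AE. If CBD lowers pain as hoped, fewer CBD patients report worsening and the CBD aggregate rows fall. An excess of other AEs on CBD would then look smaller in those rows than it is.

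A reader cannot repair the patient-level rows from the rest of the table. One patient can have several AEs, so subtracting the pain-worsening count from the any-AE count does not give the number of patients with some other AE. The term rows are not split by severity, so the mild, moderate and severe rows cannot be corrected either.

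What is at stake is how the summary rows are read. The evidence on individual harms remains in the table.

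**Working it through.** **Inputs from the documents.** SAP, Sample size and power considerations: difference of 1 point on the 0-10 pain scale, SD 2, 200 patients at 1:1, two-sided alpha 0.05, power 0.94 (and 80% with 128 patients). The documents give no AE rates, so there is no harms figure to reproduce.

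**The plan's own figure.** With 100 per arm the standardised difference is 1 / (2 × √(2/100)) = 3.54. Normal-approximation power is Φ(3.54 − 1.96) = 0.942; the exact t calculation gives 0.940. With 64 per arm these are 0.807 and 0.802. Both stated figures reproduce.

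**Assumptions added here.** The SD of 2 applies to the change in pain, which is normally distributed. Mean change is 0 on placebo and −1 on CBD. Every rise of at least k points is reported as a pain-worsening AE. Other AEs occur independently of pain worsening, in 50% of CBD and 40% of placebo patients, a true excess of 10 percentage points.

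**Step 1: probability q of a pain-worsening AE.** q = 1 − Φ((k − mean change)/2).
- k = 2: placebo 1 − Φ(1.0) = 15.9%; CBD 1 − Φ(1.5) = 6.7%; gap 9.2 percentage points.
- k = 1: placebo 1 − Φ(0.5) = 30.9%; CBD 1 − Φ(1.0) = 15.9%; gap 15.0 percentage points.

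**Step 2: the any-AE row.** With h the risk of another AE, P(any AE) = 1 − (1 − h)(1 − q).
- k = 2: CBD 1 − 0.50 × 0.933 = 53.3%; placebo 1 − 0.60 × 0.841 = 49.5%; difference **+3.8** percentage points instead of +10.
- k = 1: CBD 1 − 0.50 × 0.841 = 58.0%; placebo 1 − 0.60 × 0.691 = 58.5%; difference **−0.6** percentage points instead of +10.

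**Step 3: the event row.** With one event per affected patient and type, events per patient are h + q.
- k = 2: CBD 0.50 + 0.067 = 0.57; placebo 0.40 + 0.159 = 0.56.
- k = 1: CBD 0.50 + 0.159 = 0.66; placebo 0.40 + 0.309 = 0.71.
- Without pain worsening: 0.50 v 0.40.

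**Step 4: sensitivity of the any-AE difference (true excess always +10).**

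| Other AEs, CBD v placebo | k = 2 | k = 1 |
|---|---|---|
| 40% v 30% | +2.9 | −2.1 |
| 50% v 40% | +3.8 | −0.6 |
| 60% v 50% | +4.7 | +0.9 |
| 80% v 70% | +6.6 | +3.9 |

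If placebo patients improve by 1 point on average and CBD patients by 2, then at 50% v 40%:
- k = 2: q is 6.7% v 2.3% (placebo v CBD). The difference is (1 − 0.50 × 0.977) − (1 − 0.60 × 0.933) = 51.2% − 44.0%, or +7.1 before rounding.
- k = 1: q is 15.9% v 6.7%. The difference is +3.8.

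If there is no pain benefit, q is equal in both arms and the difference shrinks by the factor (1 − q): 10 × 0.841 = +8.4, or 10 × 0.691 = +6.9.

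**The case against.** The strongest reply is that harms are not hidden. Each worsening term has its own row by arm, next to dizziness, nausea, diarrhea, rash, palpitations and the rest. A CBD excess in any listed term shows there whatever happens to pain. Withdrawals due to AE, serious AEs and deaths have separate rows. Counting every AE regardless of suspected cause is a normal convention, physicians assess relatedness, and protocol section 15.3 plans a separate safety paper. All of this stands and limits the point to the aggregate rows. Relatedness does not close the gap, because Table 3 does not report it.

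Other limits also stand:

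- **Event row.** The term rows say only n. If that means events, a reader could obtain the event total without pain worsening by subtraction. The patient-level and severity rows would still be out of reach.
- **Direction.** Counts run to week 36. If CBD works and symptoms return after it stops, worsening AEs would be added to the CBD arm and offset the masking.
- **Reporting.** The documents do not say that every rise in score becomes an AE. The calculation assumes it.
- **No benefit.** Dilution with equal worsening in both arms is what any background event does, including the colds and Covid-19 infections in Table 3. It is not special to pain.

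A reader might infer that all three worsening terms are simply lack of efficacy and should be left out. The documents do not support that: protocol section 11.1 names tiredness and sleep problems among the commonest CBD side effects, so leaving them out could remove real drug harm and flatter CBD. Only pain worsening fits cleanly.

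**Conclusion.** The point holds for the aggregate rows of Table 3. They include worsening of the primary outcome, no total without it is planned, and the patient-level rows cannot be rebuilt from what is shown. Under the stated assumptions, a pain effect of the planned size would turn an assumed 10-point excess of other AEs (50% v 40%) into about +3.8 or −0.6 percentage points, depending on how large a rise counts as an AE. These figures illustrate a mechanism and do not predict the result. The masking needs a pain benefit, and it is weaker if placebo patients improve or symptoms return off drug.

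Two stronger readings go too far. One is that CBD would appear clearly safer than placebo. For example, worsening rates of 15% v 35% (CBD v placebo) give 57.5% v 61.0%, or −3.5 percentage points. That needs a 20-point gap in worsening AEs, while the planned effect implies about 9 to 15 points. The other is that the safety conclusion as a whole depends on the efficacy result. No AE test, safety margin or safety decision rule is planned, and the other rows still show harms by arm. This is a low-cost improvement to a descriptive table.

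**What to change.** Keep every existing row. In the SAP's Harms list and in Table 3, repeat the any-AE, event-rate and mild/moderate/severe rows with pain worsening excluded, directly beside the full versions. Define the excluded term in writing before unblinding, so that the choice cannot follow the results.

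If a version that also excludes worsening of fatigue and sleep is wanted, make it supplementary only. Label it as removing terms that protocol section 11.1 lists as common CBD side effects.

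The cost is a slightly longer table and one definition to settle. The rows come from AE data already collected.
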